#### **11.1.1.3 System Revision Risk**

The Intellis neurostimulators will provide at least 9 years of operation before replacement is recommended. It is possible that the system will need to be revised (explanted, replaced, or repositioned) earlier than 9 years. Possible reasons for revision/explant may include infection, malfunction, and migration of the system components. The risks associated with system revision are equivalent to the commercially available systems.

#### **11.1.1.4 Risks Associated with the Recharging System**

The recharger, antenna, and belt are not sterile, and contact with the wound could cause an infection. The recharger is not intended to be used on an unhealed wound. Use of rechargeable neurostimulation systems may be associated with adverse events including heating sensation, discomfort, blistering not caused by heating, skin irritation, or redness near the implanted neurostimulator during or after recharging. Subjects should check for skin irritation or redness near the neurostimulator during recharging.

#### **11.1.1.5 Study-Specific Risks**

Parameters used during the study may not be effective, which could result in an increased level of pain. Although secure electronic systems will be used, data will be anonymized, and other measures will be taken in this study to protect subject privacy there is not a guarantee of absolute confidentiality and privacy; therefore, there is a slight risk of a loss of subject privacy in case of a data breach involving a subject's protected health information.

### **11.2 Risk Minimization**

The potential risks associated with the study were assessed, identified, and have been mitigated as far as possible. Any potential risks associated with this study are further minimized by selecting qualified investigators with proper SCS therapy and device implantation experience and training study personnel on the CIP. Instructions will be given to the study participants to ensure they can properly use the patient programmer/recharger system and at any time during the study, subjects will be able to turn their device "OFF". Furthermore, a subject has the right to withdraw from the study at any time and for any reason (e.g., due to insufficient pain relief). Labeling that contains precautions, warnings, and contraindications, as well as instructions on the use of the devices are available to investigators who may provide this information to subjects.

Further mitigations reside in careful construction of the study. This includes selecting an appropriate patient population via inclusion/exclusion screening and closely monitoring subject progress and events reported for the study. Data will be anonymized, and secure electronic systems will be used for data transfer. In addition, investigators will be actively involved in the implantation and follow-up of the subjects in the study.

## **11.3 Potential Benefits**

There may be no direct medical benefit to subjects participating in the study. During the study, subjects will have increased interaction with physicians or medical staff compared to routine clinical care, which may provide some indirect health benefits. Spinal cord stimulation and the settings used during this study may reduce pain intensity, return the patient to a more fully functional status, and/or improve quality of life. These benefits cannot be guaranteed due to the investigational nature of this study.

The primary anticipated benefit of this study is to help Medtronic with the understanding of SCS therapy and assist with the design of future studies and product improvements. The information gathered from this study could also help clinicians optimize therapy for their patients.

## **11.4 Risk-Benefit Rationale**

Subjects participating in this study will be exposed to risks from commercial SCS therapy that have been deemed, through existing pre-market application approval, to be outweighed by the benefits of treating chronic, intractable pain within approved indications. Additional risks that exist due to participation in the study, including reduced efficacy and uncomfortable stimulation, are low severity, have been minimized by mitigations within the study design, and will be properly communicated to potential subjects. Based on the risk acceptance criteria for the DTM-LE SCS Study laid out in the Study Risk Management Plan, the study-specific residual risk is determined to be acceptable given the expected benefits of furthering the understanding of SCS therapy to inform future studies and product improvements outweigh these additional risks and support the conduct of this study.

# **12. Adverse Events and Device Deficiencies**

## **12.1 Adverse Events**

AE definitions are provided in [Table 12-1](#). All device-related, therapy-related, and procedure-related adverse event information will be collected throughout the study duration, starting at the time of signing the IC. Each event will be classified according to 5 different levels of causality using the following terms:

- Not related
- Unlikely
- Possible
- Probable
- Causal

Only events that are classified as possible, probable or causal are considered to be related.

Reporting of these events to Medtronic will occur on an AE Form. Each event must be reported separately. Documented pre-existing conditions are not considered AEs unless the nature or severity of the condition has worsened and meets reporting criteria. Unavoidable Adverse Events (UAE), listed in [Table 12-1](#), need not be reported unless the adverse event worsens or is present outside the stated timeframe post-implant.

For AEs that require immediate reporting (see [Table 12-3](#)), initial reporting may be done by phone, email, or on the CRF completing as much information as possible. The completed AE CRF must be submitted to Medtronic as soon as possible. Any medication/treatment associated with the treatment of an AE must be reported

Subject deaths are also required to be reported Refer to [Section 12.6](#) for Subject Death collection and reporting requirements.

## **12.2 Device Deficiency**

The DD definition is provided in [Table 12-1](#). DD information will be collected throughout the study and reported to Medtronic. Note that DD that result in an AE to the subject should be captured as an AE only.

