**Table 12-1: AE and DD Definitions**

General	
Adverse Event (AE)	
Untoward medical occurrence, unintended disease or injury, or untoward clinical signs (including abnormal laboratory findings) in subjects, users or other persons, whether or not related to the investigational medical device and whether anticipated or unanticipated
 
NOTE 1: This definition includes events related to the investigational medical device or the comparator.
 
NOTE 2: This definition includes events related to the procedures involved.
 
NOTE 3: For users or other persons, this definition is restricted to events related to investigational medical devices.
 
(ISO 14155:2020, 3.2)

Adverse Device Effect (ADE)	
AE related to the use of an investigational medical device
 
NOTE 1: This definition includes AEs resulting from insufficient or inadequate instructions for use, deployment, implantation, installation, or operation, or any malfunction of the investigational medical device.
 
NOTE 2: This definition includes any event resulting from an error use or from intentional misuse of the investigational medical device.
 
NOTE 3: this includes 'comparator' if the comparator is a medical device.
 
(ISO 14155:2020, 3.1)

Device Deficiency (DD)	
Inadequacy of a medical device with respect to its identity, quality, durability, reliability, usability, safety or performance.
 
NOTE 1: DD include malfunctions, use errors and inadequacy in the information supplied by the manufacturer including labeling.
 
NOTE2: This definition includes device deficiencies related to the investigational medical device or the comparator. (ISO 14155:2020, 3.19)

Relatedness	

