Device Related  (includes all implantable components and features, associated introduction tools, operational and installed software and programmers as defined in the CIP, see Section 7.1 )	An AE that results from the presence or performance of any component of the system.  Neurostimulator-related : An AE that results from the presence or performance (intended or otherwise) of the neurostimulator. Lead-related : An AE that results from the presence or performance (intended or otherwise) of the lead. Extension-related : An AE that results from the presence or performance (intended or otherwise) of the extension. External Study Device-related : An AE that results from the presence or performance (intended or otherwise) of an external study device (e.g., programmer, ENS).
Therapy Related	Event related to therapy delivery by device. Normally therapy-related events resolve when the device is turned off or reprogrammed. This category should not include events that resulted from a malfunction of the device (i.e. hardware-related events).
Procedure Related	An AE that occurs due to any procedure related to the implantation or surgical modification of the system.

Seriousness	
Serious Adverse Event (SAE)	
AE that led to any of the following
 
a) death, b) serious deterioration in the health of the subject, users or other persons as defined by one or more of the following: 1) a life-threatening illness or injury, or 2) a permanent impairment of a body structure or a body function, including chronic disease, or 3) in-patient or prolonged hospitalization, or 4) medical or surgical intervention to prevent life-threatening illness or injury or permanent impairment to a body structure or a body function, c) fetal distress, fetal death or a congenital abnormality or birth defect including physical or mental impairment
 
NOTE 1: Planned hospitalization for a pre-existing condition, or a procedure required by the CIP, without serious deterioration in health, is not considered an SAE. (ISO 14155:2020, 3.45)

Serious Adverse Device Effect (SADE)	Adverse device effect that has resulted in any of the consequences characteristic of a serious adverse event. (ISO 14155:2020, 3.44)

Causality	

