**14.7 Safety assessment**

To characterize all device-related, therapy-related, and procedure-related adverse events and device deficiencies from the Device Trial Start Visit until study exit. Adverse events and device deficiencies will be summarized using summary tables displaying the frequency and percentages. Adverse events will be summarized by seriousness as well.

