## 7.10 Safety Evaluation

All device-related, therapy-related, and procedure-related adverse events and device deficiencies from the Device Trial Start Visit until study exit will be characterized.

Adverse events and device deficiencies will be coded and summarized using the most recent version of Medical Dictionary for Regulatory Affairs (MedDRA).

The adverse events will also be categorized by relationship to study device and/or therapy. Adverse events will be presented in summary tables displaying the number of serious events, the number of events, and the number and percentage of subjects with one or more events. A summary of all device or therapy related adverse events and of any deaths will also be provided. A narrative of each serious device- or therapy-related adverse event will be provided.

Device deficiencies will be presented in summary tables displaying the number of deficiencies, and the number and percentage of subjects with deficiencies.

Device exposure will be summarized by analysis set and is considered from the time the subject is first exposed to the neurostimulation system (at the beginning of the device trial) until the product is explanted, or the subject discontinues from or completes the study, if later. Amount of exposure will be summarized (in months) using descriptive statistics such as mean, standard deviation, minimum, and maximum.

Data from the Scheduled Follow Up CRF will be evaluated for subjects in the Completer Analysis Set to determine whether subjects were programmed within DTM-LE limits during the study. For subjects who

were programmed within DTM-LE limits, the months of DTM-LE exposure will be computed in the same way as above, with the Cut-off Date for DTM-LE extending until the date at which it was reprogrammed out of DTM-LE limits.

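### The device deficiency table will omit deficiencies that led to an adverse event, and the SAP neither adds them back nor labels the table as restricted

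*Protocol*

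**What the plan says.** Protocol 12.2 (Device Deficiency) gives the recording rule: "Note that DD that result in an AE to the subject should be captured as an AE only".

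The definition in Protocol Table 12-1 does not depend on harm. Its first note reads: "DD include malfunctions, use errors and inadequacy in the information supplied by the manufacturer including labeling".

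The safety aim is stated in nearly the same words in both documents. Protocol 14.7: "To characterize all device-related, therapy-related, and procedure-related adverse events and device deficiencies from the Device Trial Start Visit until study exit". SAP 7.10: "All device-related, therapy-related, and procedure-related adverse events and device deficiencies from the Device Trial Start Visit until study exit will be characterized".

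On output, Protocol 14.7 says: "Adverse events and device deficiencies will be summarized using summary tables displaying the frequency and percentages". SAP 7.10 is more specific: "Device deficiencies will be presented in summary tables displaying the number of deficiencies, and the number and percentage of subjects with deficiencies". For adverse events it adds: "The adverse events will also be categorized by relationship to study device and/or therapy".

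**The concern.** A malfunction that injures a subject is a deficiency by definition, but under the recording rule it has no deficiency record. The SAP builds its deficiency table without saying how such cases are handled. A reader of the study report would naturally take that table as the complete tally of device problems, when it holds only those that did not result in an AE to the subject.

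What is at stake is one descriptive safety count and its subject percentage. The primary endpoint, the secondary endpoint and the sample size are untouched.

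**Working it through.** The documents state no deficiency count or rate, so there is no plan figure to reproduce. The check sets the passages side by side and follows a deficiency from its occurrence to the table.

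1. **Is a deficiency that causes harm still a deficiency?** Yes. The definition in Table 12-1 concerns inadequacy of the device and makes no reference to consequences.

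2. **Where is it recorded?** On the AE form only, under Protocol 12.2.

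3. **Does the deficiency table bring it back?** Not as written. Neither Protocol 14.7 nor SAP 7.10 describes drawing on AE records for the deficiency table, and neither restricts the table to deficiencies without an AE.

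4. **Can the planned AE tables show it?** Not as a deficiency. SAP 7.10 sorts AEs by relationship to device and/or therapy. Table 12-1 defines device-related as "An AE that results from the presence or performance of any component of the system". This puts an AE from a correctly working component in the same category as an AE from a faulty one. Protocol Table 12-2 lists what is classified for each AE: relatedness, seriousness and diagnosis. None of these names a deficiency as the cause.

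5. **What does each reported measure lose?** Let D be all deficiencies and H those that resulted in an AE to the subject. Let S be the subjects with at least one deficiency, S_H the subjects whose every deficiency falls in H, and N the denominator.

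   - Deficiency count: the table shows D − H instead of D.
   - Subject percentage: the table shows 100 × (S − S_H)/N instead of 100 × S/N. The ratio of shown to full is 1 − S_H/S.

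   The two losses differ. A subject with one harmless and one harmful deficiency contributes 1 instead of 2 to the count but stays in the percentage. A subject whose single deficiency was harmful contributes 0 instead of 1 and drops out of both.

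6. **How large is the loss?** H and S_H are not given and cannot be inferred. With S_H/S between 0 and 1, the percentage shown runs from the full value to zero. The rule can lower these measures but never raise them.

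7. **Which denominator?** The SAP sentence on deficiencies names none, and the text under SAP 7.1 that would hold the analysis sets is redacted, so no fault is alleged there. Safety is characterised from the Device Trial Start Visit, and both Protocol 7.5 and SAP 7.10 date device exposure from the start of the device trial. Subjects who were trialed but never implanted are therefore also at risk of a deficiency.

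**The case against.** The strongest reply is that nothing harmful is hidden. A deficiency that injures a subject should appear as a device-related AE. Table 12-1 keeps malfunction events out of the therapy-related category and splits device-related AEs by component. SAP 7.10 summarises all device- or therapy-related AEs and gives a narrative for each serious one. Single capture is a deliberate way to avoid counting one event twice, and safety is descriptive, with no threshold on a deficiency rate. The sponsor also reviews every AE and deficiency (Protocol 12.5.1), meets regularly to look for trends (section 13) and receives product complaints separately (12.7).

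All of this stands, and it rules out several stronger readings that a reader might infer:

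- **Harmful deficiencies vanish from safety reporting.** They do not. They lose only their identity as deficiencies.
- **The subject percentage excludes every subject with a harmful deficiency.** It does not. It loses only subjects with no other deficiency.
- **The rule covers all harm.** It is limited to an AE to the subject, so a deficiency that harmed a user or another person is not removed by it.
- **The AE form has no field for this.** Unknown. The form is not among the public documents. What can be said is that the visible SAP text plans no analysis of such a field.
- **Some deficiencies appear in neither table, through the exemption for unavoidable AEs in Protocol 12.1.** This is a weak inference. Those events are defined as inherent to the surgery and expected in all subjects, which hardly describes the result of a device fault.

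The reply does not repair the table. Presence and performance share one category, so a reader of the planned outputs cannot reconstruct the full deficiency count.

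**Conclusion.** The point holds as an incomplete count produced by a stated rule. The planned number of deficiencies omits all that caused an AE to the subject, and the planned subject percentage omits subjects who had only such deficiencies. The direction is certain (down or unchanged). The size is not derivable, and no illustrative rate should be attached to it.

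This assumes that sites follow Protocol 12.2 literally and that no redacted text adds the cases back. The weight is low: it affects the completeness and labelling of one descriptive table, not a planned inference.

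**What to change.** Keep one form per event. Identify AEs that resulted from a device deficiency, either by a flag on the AE form if none exists or as a recorded item in the sponsor's existing AE and deficiency review. In SAP 7.10, report:

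- (a) deficiencies without an AE;
- (b) AEs resulting from a deficiency;
- (c) the number and percentage of subjects with either, with subjects who started the device trial as the denominator.

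Rows (a) and (b) should not simply be added to give a total of deficiencies. Protocol 12.1 has each AE reported separately, so one deficiency may generate several AE records. Row (c) avoids that problem.

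At minimum, title the existing table as device deficiencies not resulting in an AE. That needs no new data.

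The cost of the full change is one field or review step and one or two table rows. Records already entered would need a single look back through the device-related AEs.

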## **12.3 Processing Updates and Resolution**

For any changes in status of a previously reported AE or DD (i.e. change in actions taken, change in outcome, change in relatedness), information needs to be updated on, or added to the original AE or DD form. All AEs must be followed until the AE has been resolved, is unresolved with no further actions planned, the subject dies or exits the study, or until study closure, whichever occurs first.

At the time of study exit, all collected adverse events that are unresolved must be reviewed and an update to the original AE must be reported.

## **12.4 Definitions/Classifications**

Where the definition indicates "device", it refers to any device used in the study.

**Table 12-1: AE and DD Definitions**

General	
Adverse Event (AE)	
Untoward medical occurrence, unintended disease or injury, or untoward clinical signs (including abnormal laboratory findings) in subjects, users or other persons, whether or not related to the investigational medical device and whether anticipated or unanticipated
 
NOTE 1: This definition includes events related to the investigational medical device or the comparator.
 
NOTE 2: This definition includes events related to the procedures involved.
 
NOTE 3: For users or other persons, this definition is restricted to events related to investigational medical devices.
 
(ISO 14155:2020, 3.2)

Adverse Device Effect (ADE)	
AE related to the use of an investigational medical device
 
NOTE 1: This definition includes AEs resulting from insufficient or inadequate instructions for use, deployment, implantation, installation, or operation, or any malfunction of the investigational medical device.
 
NOTE 2: This definition includes any event resulting from an error use or from intentional misuse of the investigational medical device.
 
NOTE 3: this includes 'comparator' if the comparator is a medical device.
 
(ISO 14155:2020, 3.1)

Device Deficiency (DD)	
Inadequacy of a medical device with respect to its identity, quality, durability, reliability, usability, safety or performance.
 
NOTE 1: DD include malfunctions, use errors and inadequacy in the information supplied by the manufacturer including labeling.
 
NOTE2: This definition includes device deficiencies related to the investigational medical device or the comparator. (ISO 14155:2020, 3.19)

Relatedness	
Device Related  (includes all implantable components and features, associated introduction tools, operational and installed software and programmers as defined in the CIP, see Section 7.1 )	An AE that results from the presence or performance of any component of the system.  Neurostimulator-related : An AE that results from the presence or performance (intended or otherwise) of the neurostimulator. Lead-related : An AE that results from the presence or performance (intended or otherwise) of the lead. Extension-related : An AE that results from the presence or performance (intended or otherwise) of the extension. External Study Device-related : An AE that results from the presence or performance (intended or otherwise) of an external study device (e.g., programmer, ENS).
Therapy Related	Event related to therapy delivery by device. Normally therapy-related events resolve when the device is turned off or reprogrammed. This category should not include events that resulted from a malfunction of the device (i.e. hardware-related events).
Procedure Related	An AE that occurs due to any procedure related to the implantation or surgical modification of the system.

Seriousness	
Serious Adverse Event (SAE)	
AE that led to any of the following
 
a) death, b) serious deterioration in the health of the subject, users or other persons as defined by one or more of the following: 1) a life-threatening illness or injury, or 2) a permanent impairment of a body structure or a body function, including chronic disease, or 3) in-patient or prolonged hospitalization, or 4) medical or surgical intervention to prevent life-threatening illness or injury or permanent impairment to a body structure or a body function, c) fetal distress, fetal death or a congenital abnormality or birth defect including physical or mental impairment
 
NOTE 1: Planned hospitalization for a pre-existing condition, or a procedure required by the CIP, without serious deterioration in health, is not considered an SAE. (ISO 14155:2020, 3.45)

Serious Adverse Device Effect (SADE)	Adverse device effect that has resulted in any of the consequences characteristic of a serious adverse event. (ISO 14155:2020, 3.44)

Causality	
Not Related	
Relationship to the device or procedures can be excluded when:
 
 
– the event is not a known side effect of the product category the device belongs to or of similar devices and procedures;
 
– the event has no temporal relationship with the use of the investigational device or the procedures;
 
– the serious event does not follow a known response pattern to the medical device (if the response pattern is previously known) and is biologically implausible;
 
– the discontinuation of medical device application or the reduction of the
 
– level of activation/exposure - when clinically feasible – and reintroduction of its use (or increase of the level of activation/exposure), do not impact on the serious event;
 
– the event involves a body-site or an organ not expected to be affected by the device or procedure;
 
– the serious event can be attributed to another cause (e.g. an underlying or concurrent illness/ clinical condition, an effect of another device, drug, treatment or other risk factors);
 
– the event does not depend on a false result given by the investigational device used for diagnosis, when applicable;
 
– harms to the subject are not clearly due to use error;
 
– In order to establish the non-relatedness, not all the criteria listed above might be met at the same time, depending on the type of device/procedures and the serious event.
 

Unlikely	
The relationship with the use of the device seems not relevant and/or the event can be reasonably explained by another cause, but additional information may be obtained.

Possible	
The relationship with the use of the investigational device is weak but cannot be ruled out completely. Alternative causes are also possible (e.g. an underlying or concurrent illness/ clinical condition or/and an effect of another device, drug or treatment). Cases where relatedness cannot be assessed or no information has been obtained should also be classified as possible.

Probable	
The relationship with the use of the investigational device seems relevant and/or the event cannot reasonably explained by another cause, but additional information may be obtained.

Casual Relationship	
The serious event is associated with the investigational device or with procedures beyond reasonable doubt when:
 
 
– the event is a known side effect of the product category the device belongs to or of similar devices and procedures;
 
– the event has a temporal relationship with investigational device use/application or procedures;
 
– the event involves a body-site or organ that
 
– the investigational device or procedures are applied to;
 
– the investigational device or procedures have an effect on;
 
– the serious event follows a known response pattern to the medical device (if the response pattern is previously known);
 
– the discontinuation of medical device application (or reduction of the level of activation/exposure) and reintroduction of its use (or increase of the level of activation/exposure), impact on the serious event (when clinically feasible);
 
– other possible causes (e.g. an underlying or concurrent illness/ clinical condition or/and an effect of another device, drug or treatment) have been adequately ruled out;
 
– harm to the subject is due to error in use;
 
– the event depends on a false result given by the investigational device used for diagnosis, when applicable;
 
– In order to establish the relatedness, not all the criteria listed above might be met at the same time, depending on the type of device/procedures and the serious event.
 

If an investigational device gives an incorrect diagnosis, the patient might, for example, receive an unnecessary treatment and incur all the risks that accompany that treatment, or might be incorrectly diagnosed with a serious disease. In other cases, the patient might not receive an effective treatment (thereby missing out on the benefits that treatment would confer), or might not be diagnosed with the correct disease or condition.

Other	
Unavoidable Adverse Event (UAE)	An AE inherent to a surgical procedure that is expected to occur in all subjects for a projected duration according to the Investigator's opinion, including, but not limited to:
Event Description	Timeframe from Surgical Procedure
Anesthesia related nausea / vomiting	24 hours
Low-grade fever (<100°F or 37.8°C)	48 hours
Seroma	72 hours
Sleep problems (insomnia)	72 hours
Back pain/discomfort/stiffness related to laying on table	72 hours
Mild to moderate bruising / ecchymosis	7 days
Pocket site / Incisional pain	7 days

